RESEARCH PROTOCOL

Single lung ventilation refers to the situation in which one lung is ventilated and the other lung is deflated, mechanically separating the two lobes of the lung. Single lung ventilation is performed to facilitate surgical access in intrathoracic procedures involving the lung, esophagus, anterior mediastinal structures, and aorta, as well as in selected orthopedic spine procedures (1). There are three types of lung isolation methods; 1. Double-lumen endobronchial tube, 2. Broach blocker, 3. Single-lumen endobronchial tube (2). The most commonly used method for single-lung ventilation is intubation with a double-lumen endobronchial tube (3), (4). Double-lumen tubes allow isolation of both lungs, selective ventilation, and intermittent suctioning. A double-lumen tube has separate tracheal and bronchial lumens; it is essentially two tubes connected side by side. The shorter tube has a high-volume, low-pressure tracheal head and forms the tracheal lumen positioned just above the carina. In both left and right double-lumen tubes, the smaller, low-volume, high-pressure bronchial cuff is ideally positioned just below the tracheal carina and before the division of the lobar bronchus. The cuffs pilot balloons and the connection areas at the top of each of the two tubes are all color-coded (white for the tracheal tube and blue for the endobronchial tube). When the double-lumen tubes are properly positioned, both the tracheal and bronchial cuffs are inflated, clamping the lumen of the opposite lung to provide selective single-lung ventilation. Left double-lumen tubes are most often selected because of the longer left main bronchus, easier positioning, and greater margin of error compared to right double-lumen tubes. The length of the left bronchus is 4-6 cm in men and 3-5 cm in women, while the length of the right main bronchus is 1-2 cm. It is more difficult to maintain the position of right double-lumen tubes than left double-lumen tubes, therefore complications due to incorrect positioning may be more common. For these reasons, the use of right double-lumen tubes is limited to special situations. These are; left pneumonectomy, distorted anatomy of the left main bronchus entrance due to external and intraluminal compression, and the surgical site containing the left main bronchus. Placement of left double-lumen tubes is generally easier than right double-lumen tubes. Under direct laryngoscopy, the endobronchial tip is inserted between the vocal cords, the stylet is removed, and the double-lumen tube is rotated 90 degrees to the left while advancing. Airway damage (hoarseness, sore throat, tracheal rupture) and hypoxemia may occur due to incorrect positioning of the double-lumen tube (5). Traditionally, the position of the left double-lumen tube is confirmed by auscultation. Initial auscultation is performed with both tracheal and bronchial cuffs inflated; if the double-lumen tube is properly inserted, ventilation through both lumens should result in equal bilateral breath sounds. The tracheal lumen is then clamped and ventilation should result in breath sounds on the left side but not the right. The bronchial lumen is then clamped and ventilation should result in breath sounds on the right side but not the left. Fiberoptic bronchoscopy is the gold standard for confirming the position of double-lumen tubes (6). If the left double-lumen tube is ideally positioned, the initial bronchoscopic view through the tracheal lumen will show a blue bronchial balloon visible just beyond the carina on the left side without herniation into the trachea. The tube is then confirmed by advancing the bronchoscope into the bronchial lumen to ensure that the bronchial tube has not been advanced too far. The video double lumen tube, which has been used in recent years, is a technique where the tube location can be continuously seen on the screen during the application and surgery, but it has not become very widespread yet (7), (8). The primary purpose of this study is to investigate the superiority, advantages and disadvantages of these techniques used for the correct and short-term positioning of the double lumen tube in single lung ventilation. The secondary purpose is to determine the method that will ensure that the tube location can be verified in the shortest time and that intraoperative location changes can be detected in a short time, and that complications that may occur due to incorrect placement of the double lumen tube can be prevented, thus reducing complications. Other purposes are to perform the intubation procedure with the double lumen tube in the shortest time and verify its location in the shortest time, to save time, to prevent complications by detecting tube location changes in the intraoperative period in the shortest time, and thus to provide the shortest and safest operation time. Shortening the duration and preventing complications will also reduce costs. Although it has been stated in the literature that video double

RESEARCH PROTOCOL

lumen tubes are cost effective, their superiority over other techniques has not been demonstrated because their use has not yet become widespread. Another aim of the study is to compare the cost effects of these three methods.

Using the studies in the literature, the total number of patients for three groups was found to be 93 by using G-power to calculate the sample size and taking the effect size as 0.33 at a 95% confidence level and 80% power.

In Kayseri City Hospital, ASA I-III patients aged 18-84 who are planned to undergo surgery with single lung ventilation between December 2024 and May 2025 will be included in the study after obtaining their informed consent. In our hospital, video double lumen tube verification techniques, and auscultation and fiberoptic bronchoscopy are routinely used for conventional double lumen tubes. Patients are blinded in terms of the method to be applied, and since the anesthesiologist who will perform the intubation procedure is the person who performs the method, blinding cannot be performed. Anesthesiologists who perform the intubation procedure will not have any information about the study. They will use the method they prefer. Patient randomization will be done in this way. In the study, volunteers were blinded because they did not know which intubation method would be used, while blinding could not be done for the anesthesiologist who would perform the intubation. Due to the advantages mentioned above, a left tube will be used in all patients. Tube sizes will be determined according to the height and gender of the patients. Group I will be divided into three groups randomly as patients whose tube location will be confirmed by auscultation, Group II patients whose tube location will be confirmed by using fiberoptic bronchoscopy, and Group III patients whose tube location will be confirmed by using a video-guided double-lumen intubation tube. After the patients are taken to the operating room, routine monitoring will be applied and vascular access will be established with an 18G intravenous catheter. After preoxygenation with 100% O₂ for 2 minutes, anesthesia induction will be applied with 2-3 mg/kg propofol, 1-2 mcg/kg fentanyl, and 0.6mg/kg rocuronium. They will be ventilated with 100% oxygen until neuromuscular blockade occurs for at least 2 minutes. The intubation duration will be started after the vocal cords are visualized with the laryngoscope and will be taken as the time until end tidal CO₂ is seen on the monitor. Intubation verification time was planned for Group I as the time when bilateral respiratory sounds are heard while both cuffs are inflated, then the tracheal lumen is clamped and no respiratory sounds are heard on the right, respiratory sounds are heard on the left and then the bronchial lumen is clamped and no respiratory sounds are heard in the left lung, and respiratory sounds are confirmed to be heard in the right lung. For Group II, it was planned to be taken as the time when the fiberoptic bronchoscope is first entered into the tracheal lumen and the carina and bronchial blue-colored cuff is seen to be inflated without herniation in the left bronchus and then entered through the left bronchial lumen and it is seen that the tube is not advanced too much. III. In the group, it was planned to be taken as the time when the bronchial lumen of the video double lumen tube entered the left bronchus and the blue cuff was inflated. After the patients were given the lateral decubitus position with the lung to be operated on top, the tube location for each group was confirmed again and the time was recorded. Anesthesia maintenance will be provided using 1 MAC sevoflurane. The number of intubation attempts in the 3 groups, the duration of intubation, the duration of tube location verification, the quality of lung collapse, the need for fiberoptic bronchoscopy, the duration of fiberoptic bronchoscopy, the number of tube dislocations, and the duration of dislocation correction will be monitored. After extubation, the patients will be taken to the recovery room. In the recovery room, the patients will be questioned about the presence of sore throat and hoarseness. The methods used in the patients will be compared in terms of cost according to the type of tube and the use of fiberoptic. The data to be collected for the study will be recorded using the SPSS 22 program and analyzed in the same program. Frequency, percentage, mean value, standard deviation, maximum and minimum (min-max) values will be used for descriptive statistics, Pearson Chi-square test will be applied for statistical analysis of categorical data and Fisher's Exact Test will be applied for values below five in four-sided tables.

RESEARCH PROTOCOL

The conformity of quantitative data to normal distribution will be tested with the Kolmogorov-Smirnov and Shapiro Wilk tests. For statistical analysis of quantitative data in independent groups, Unpaired t test and One-Way Anova test (post hoc Tukey test) will be used for data conforming to normal distribution, Mann-Whitney U, Kruskall-Wallis test and Pearson Correlation coefficient will be used to show the relationship between variables for data not conforming to normal distribution. Statistical significance of the difference was accepted as p<0.05.

SOURCES:

1. Mehrotra, M. and A. Jain, Single-Lung Ventilation, in StatPearls [Internet]. 2023, StatPearls Publishing.
2. Hickey, S.M. and A.O.J.T.I.S.P. Giwa, Mechanical ventilation. 2020.
3. Morgan, G. and M.J.K.A. Mikhail, MurrayMJ. 2002: p. 1040-2.
4. Campos JH. Current techniques for perioperative lung isolation in adults. *Anesthesiology*. 2002; 97:1295–1301.
5. Liu, S., Y. Mao, P. Qiu, et al., Airway rupture caused by double-lumen tubes: A review of 187 cases. 2020. 131(5): p. 1485-1490.
6. Campos JH. Which device should be considered the best for lung isolation: double-lumen endotracheal tube versus bronchial blockers. *Current Opinion in Anesthesiology*2007
8. The Video Double-Lumen Endobronchial Tube: Is the Benefit Worth the Cost? *Journal of Cardiothoracic and Vascular Anesthesia* 32 (2018) 275–276

RESPONSIBLE RESEARCHER: Doc. Dr. [name]

ASSISTANT RESEARCHER: [name] [name]

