STATISTICAL ANALYSIS

The data to be collected for the study will be recorded using SPSS 22 program and analyzed in the same program. Frequency, percentage, mean value, standard deviation, maximum and minimum (min-max) values will be used for descriptive statistics, Pearson Chi square test will be applied for statistical analysis of categorical data and Fisher's Exact Test will be applied for values below five in four-sided tables. The conformity of quantitative data to normal distribution will be tested with Kolmogorov-Smirnov and Shapiro Wilk tests. For statistical analysis of quantitative data in independent groups, Unpaired t test and One-Way Anova test (post hoc Tukey test) will be used for data conforming to normal distribution, Mann-Whitney U, Kruskall-Wallis test will be used for data not conforming to normal distribution and Pearson Correlation coefficient will be used to show the relationship between variables. Statistical significance of the difference was accepted as $p < 0.05$.

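### Allocation follows the anaesthesiologist's preference but is called randomization, so technique can be confounded with operator and patient, and the planned unadjusted tests cannot separate them

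*Protocol*

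**What the plan says.** The methods paragraph of the protocol makes two statements about how patients reach their group. The first gives a mechanism: "They will use the method they prefer. Patient randomization will be done in this way". The second, a few sentences later, gives only a label: "Group I will be divided into three groups randomly as patients whose tube location will be confirmed by auscultation", with the fibreoptic and video groups following. Neither document describes a sequence, an allocation ratio, stratification or concealment.

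Operators are to be kept unaware of the study: "Anesthesiologists who perform the intubation procedure will not have any information about the study". They are not blinded to technique: "since the anesthesiologist who will perform the intubation procedure is the person who performs the method, blinding cannot be performed". The same paragraph says the video tube is in routine use at the hospital and that "auscultation and fiberoptic bronchoscopy are routinely used for conventional double lumen tubes".

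The aim is comparative: "The primary purpose of this study is to investigate the superiority, advantages and disadvantages of these techniques". On sample size, "the total number of patients for three groups was found to be 93".

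The SAP names only tests in which group is the sole factor. For normal data, "For statistical analysis of quantitative data in independent groups, Unpaired t test and One-Way Anova test (post hoc Tukey test) will be used"; for non-normal data, Mann-Whitney and Kruskal-Wallis; for categorical data, chi-square or Fisher. Pearson correlation is added to describe relationships between variables. The protocol lists the same tests.

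**The concern.** Randomization matters because it makes the assigned technique independent of everything else that affects the outcome. Preference does the opposite. An anaesthesiologist may reach for the video tube when a difficult airway is expected, or use auscultation out of long habit. Expected airway difficulty, type of surgery and operator skill can all affect the number of attempts, both timed intervals and tube displacement. Eligibility is wide (ASA I to III, ages 18 to 84), so there is room for case mix to differ between groups.

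The planned tests compare raw group means, ranks or proportions and treat all patients as independent. With no plan to record the operator, adjustment for operator could not be added later from the planned data. A difference due to who was intubated, or by whom, would be attributed to the technique, and the protocol's wording invites its report as a randomised result.

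**Working it through.** **1. The text.** Set side by side, one statement names a mechanism (preference) and the other a property (random division). The second supplies nothing that could produce randomness, so it contradicts the first without replacing it. That method can be confounded follows from this alone. The remaining steps show what could be at stake.

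**2. The plan's sample size.** Inputs from the protocol: effect size 0.33 (metric not named; read as Cohen's f), alpha 0.05, power 80%, three groups. For one-way ANOVA the noncentrality is λ = N·f².

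- N = 90: λ = 90 × 0.1089 = 9.80, power 0.793.
- N = 93: λ = 93 × 0.1089 = 10.13, power 0.807.

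So 93 is the smallest total with equal groups that reaches 80%. The arithmetic is right, but it presumes 31/31/31 and independent patients.

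**3. Unequal groups.** The means are held at values that give f = 0.33 with equal groups. If one arm differs from the other two by δ (in SD), then δ² = 0.1089 × 9/2 = 0.490 and λ = n₁(N − n₁)/N × δ², where n₁ is the size of that arm. The splits below are assumed.

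- 40/40/13, arm of 13 differs: λ = 13 × 80/93 × 0.490 = 5.48, power 0.529.
- 40/40/13, an arm of 40 differs: λ = 40 × 53/93 × 0.490 = 11.17, power 0.846.
- 45/38/10, arm of 10 differs: λ = 10 × 83/93 × 0.490 = 4.37, power 0.436.

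Over all patterns of means:

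| Split | Power |
|---|---|
| 31/31/31 | 0.807 |
| 32/31/30 | 0.80–0.81 |
| 36/31/26 | 0.76–0.84 |
| 40/40/13 | 0.53–0.90 |
| 45/38/10 | 0.44–0.91 |

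Mild imbalance hardly matters. Strong imbalance can lose or gain power.

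**4. Operator confounding.** Assumptions, none from the documents: 93 patients, a normal outcome, no true method effect, an operator intraclass correlation (ICC) of 0.05, 0.10 or 0.20, and unadjusted ANOVA at 5%. There were 8,000 simulations per cell. In the two-thirds row, half of each operator's patients get the favourite method and half get one of the three at random.

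| Scenario | ICC 0.05 | 0.10 | 0.20 |
|---|---|---|---|
| 9 operators, choice unrelated to operator | 0.054 | 0.045 | 0.048 |
| 9 operators, favourite in two thirds of patients | 0.066 | 0.087 | 0.127 |
| 9 operators, one method each | 0.128 | 0.219 | 0.374 |
| 6 operators, one method each | 0.170 | 0.312 | 0.480 |
| 15 operators, one method each | 0.094 | 0.143 | 0.233 |

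The one-method rows can be checked by hand. With equal caseloads m = 93/operators, the variance of a group mean is inflated by D = 1 + (m − 1)·ICC, and the rejection rate is roughly 0.05^(1/D). For 9 operators m = 10.33, so D = 1.467, 1.933 and 2.867, which gives 0.130, 0.212 and 0.352. These are close to the simulated values.

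**5. Patient confounding.** Assume that 30% of patients are difficult and that their outcome is worse by 0.5 to 1.0 SD. The spurious video-minus-auscultation difference is that amount times the gap in the share of difficult patients between the two groups.

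- Mild tilt: video is chosen in 50% of difficult and 25% of easy patients, auscultation in 20% and 40%. The difficult share is 0.15/0.325 = 0.462 with video and 0.06/0.34 = 0.176 with auscultation. The gap of 0.285 gives a bias of 0.14–0.29 SD; simulated type I error is 0.08–0.13.
- Strong tilt: video 70% and 18%, auscultation 5% and 45%. The shares are 0.21/0.336 = 0.625 and 0.015/0.33 = 0.045. The gap of 0.580 gives a bias of 0.29–0.58 SD; simulated type I error is 0.16–0.46.
- No tilt: bias about 0, type I error about 0.05.

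**6. Random allocation.** With 31 per group allocated at random, and operator effects still present (6 or 12 operators, same ICCs), the unadjusted ANOVA rejected in 0.046–0.053 of simulations. Randomization alone removes the problem in step 4.

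**The case against.** The best defence is that this is in effect a pragmatic comparison of techniques already in routine use, and that operators who know nothing of the study cannot steer patients to suit its hypothesis. That is fair as far as it goes: deliberate steering becomes less likely. Habit, device skill and response to the individual patient remain, and these are the usual sources of confounding. If an observational comparison is what is meant, the label, the superiority aim and the analysis need to say so.

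It can also be said that the simulated error rates rest on invented operator numbers, ICCs and strengths of preference, and the power ranges on invented splits. That stands. The figures show what is possible, not what is expected, and power is the lesser issue because unequal groups are not in themselves an error.

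Some aims are less exposed. Description within each group is little affected, and so is the tube-price part of the cost comparison. The part of cost that depends on fibreoptic use is not protected, since operator and patient can influence that use.

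**Conclusion.** The concern holds and must be fixed. The plan claims a safeguard that its own mechanism does not provide, and causal statements of superiority are not supported by the design and tests as written. This rests on the text, not on the simulations.

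The size of the bias cannot be derived from the documents. Under the stated assumptions the type I error of the nominal 5% test ranges from about 5%, when choice is unrelated to operator, to 48%, with six single-method operators at ICC 0.20. The total of 93 is sound for equal groups of independent patients, but the stated 80% power is not guaranteed under preference allocation.

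**What to change.** **Preferred: randomise.** Replace the two preference sentences with wording such as:

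> *Patients will be allocated 1:1:1 to Group I, II or III (31 per group) from a computer-generated list in permuted blocks of varying size, concealed in sequentially numbered opaque sealed envelopes opened after consent and before the tube is prepared.*

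Hold the block sizes outside the protocol and avoid relying on very small blocks: operators are unblinded at a single hospital, and the last place in a block of 3 can be deduced from the first two. Delete the sentence that keeps operators uninformed, and correct the sentence that describes Group I as being divided into three. N stays at 93. The cost is an amendment, a list and envelopes. The real price is that operators must know of the study and accept the assigned method; routine use of the techniques at the hospital suggests this is feasible.

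**Fallback: keep preference and say so.** This is also the route if enrolment has already taken place.

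- Remove every claim of randomization, describe a non-randomised comparison, and limit conclusions to association.
- Record the operator and operator experience, expected airway difficulty and type of surgery.
- Prespecify a regression model adjusting for these and for age, sex, ASA class and height or tube size.
- Account for operator where operators use more than one method. If each uses only one, state that operator and method cannot be separated.
- Restate power for the group sizes expected.

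This costs wording, a few extra recorded variables and a model. It reduces confounding by measured factors but does not remove confounding.

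### Anaesthetists choose and perform the method, yet the analysis has no operator term: operator differences may be reported as method differences and the 5% error rate may not hold

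*Protocol*

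**What the plan says.** **Allocation (Protocol, paragraph on patients, allocation and procedures).** The choice of method is left to the anaesthetist: "They will use the method they prefer". The next sentence presents this as the way patients are randomised. The same paragraph says "Anesthesiologists who perform the intubation procedure will not have any information about the study", and that the person who intubates is the person who carries out the method. Further on, it describes the three groups as formed at random. The two descriptions conflict.

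**Outcomes (same paragraph).** These include the number of attempts and the times for intubation, verification and correction of a dislocated tube. All of them are produced by the operator.

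**Analysis (Protocol, statistical paragraph; SAP, Statistical Analysis).** "For statistical analysis of quantitative data in independent groups", both documents plan the t test, one-way ANOVA with Tukey, Mann-Whitney and Kruskal-Wallis. Categorical outcomes go to chi-square or Fisher's exact test.

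**Sample size (Protocol).** "the total number of patients for three groups was found to be 93 by using G-power", "taking the effect size as 0.33 at a 95% confidence level and 80% power".

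Neither document states how many anaesthetists take part, says that operator or experience is recorded, or plans a block, covariate, mixed model, stratified test or design effect.

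**The concern.** The protocol wants to know which technique places and verifies the tube fastest. One person both selects the group and generates the times. Two things can then go wrong.

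- **Bias.** If quicker anaesthetists lean towards one method, their speed is credited to that method. A larger sample does not cure this.
- **Precision.** Even if preference is unrelated to skill, patients treated by the same operator tend to resemble each other. When operators concentrate in particular groups, the planned tests understate the standard error of the group comparison.

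In either case, a difference between a few operators could be published as a difference between verification techniques.

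**Working it through.** **1. The plan's own figure.** Read 0.33 as Cohen's f for a three-group one-way ANOVA, alpha 0.05. The noncentrality is N × f² = 93 × 0.33² = 93 × 0.1089 = 10.13, on 2 and 90 degrees of freedom, which gives power 0.807. The smallest N reaching 80% is 92, and equal groups of 31 make 93. Other readings do not give 93: Cohen's w with 2 df gives 89 in total, and a two-group d gives 145 per arm. So 93 is arithmetically sound, but it is the size for 93 independent patients.

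**2. Inputs that the documents do not give (assumptions).** Number of operators: 6 to 30. Intraclass correlation (ICC) within operator: 0.05 to 0.20. Strength of preference: from none (each method 33%) to exclusive use of one method.

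**3. Design effect if each operator keeps to one method.** Patients per operator m = 31 / (operators per method), and design effect = 1 + (m − 1) × ICC. Example with 3 operators per method and ICC 0.10: m = 10.33, design effect = 1 + 9.33 × 0.10 = 1.93, effective N = 93 / 1.93 = 48, and the true standard error is √1.93 = 1.39 times the one reported.

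**4. Simulated rejection rate of the planned ANOVA, no method effect, N = 93, full nesting.** The last column is the power of a valid operator-level F test at f = 0.33, with 3 × (operators per method − 1) denominator degrees of freedom.

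| Operators (per method) | ICC | ANOVA rejects | Operator-level power |
|---|---|---|---|
| 30 (10) | 0.05 | 6.7% | 73% |
| 15 (5) | 0.05 | 9.0% | 60% |
| 12 (4) | 0.05 | 10.7% | 54% |
| 9 (3) | 0.10 | 22% | 34% |
| 6 (2) | 0.20 | 49% | 14% |

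**5. Same ANOVA, partial preference.** Columns show how often an operator uses the preferred method.

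| Operators | ICC | 33% (none) | 50% | 70% | 90% |
|---|---|---|---|---|---|
| 15 | 0.05 | 4.9% | 5.2% | 7.1% | 8.2% |
| 9 | 0.10 | 4.6% | 5.9% | 9.4% | 17.3% |
| 6 | 0.20 | 5.1% | 8.1% | 21.0% | 41.6% |

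With 30 operators, ICC 0.05 and 70% preference the rate is about 5%. If operators use all three methods in exact balance, the ANOVA becomes slightly conservative (5 operators, ICC 0.10: 4.0%).

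**6. Does an operator term repair it?** In the 70% case, operator as a fixed block brings the rate back to 4% to 6%. Under full nesting, an analysis of operator means gives about 4% to 5%. A random-intercept model with an ordinary Wald test does not hold the level in the nested scenarios with 12, 9 and 6 operators: it rejects in about 7%, 10% and 18%. With small-sample degrees of freedom these become about 4%, 5% and 6.5%.

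**7. If patients are truly randomised within 9 operators.** Blocking raises power from about 81% to between 84% and 87% at ICC 0.20. At ICC 0.30 it goes from between 81% and 83% to between 89% and 92%. The ranges reflect how the within-operator allocation is simulated.

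**The case against.** The strongest reply is that the harm is conditional. It needs few operators, preferences that differ between them, and correlated outcomes within operator, and the documents establish none of these. The protocol says that all three techniques are in routine use at the hospital, which fits anaesthetists who use several. Choice could also be made case by case. With no systematic preference the planned ANOVA holds its level, and the largest inflation needs two operators per method, exclusive use and a high ICC all at once. This stands, and it is why the point is worded with *may*.

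A reader might infer that operator skill **is** being counted as a method effect and that the intervals **are** too narrow. The documents do not support that: they describe an allocation rule that permits it, without the figures that would show it. Nor do they support taking 50% as the expected error rate, or reading 93 as a miscalculation.

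It can also be said that the root defect is the allocation, and that true randomisation would remove the inflation. That is right as far as error rates go. But if preference allocation stays, the operator term is the main protection the analysis can offer. If it goes, the operator record still gives a modest gain in power.

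Finally, a random intercept does not fully remove confounding when preference tracks skill, because it still uses between-operator information. That stands, and it determines the order of preference in the fix.

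**Conclusion.** The concern holds in conditional form. Under the preference rule as written, patients are clustered within operators who may be tied to groups, and neither document allows for it. The ANOVA's false-positive rate at N = 93 then lies between about 5% (no systematic preference, or many operators) and about 20% (70% preference, six operators, ICC 0.20). It reaches about 50% only with full nesting, six operators and ICC 0.20. Operator numbers, ICCs and strength of preference are all assumptions.

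These simulations draw operator effects independently of preference. If skill and preference are linked there is also bias, whose size cannot be estimated from the documents. The stated 80% power rests on independent patients and does not carry over if operators are nested in methods.

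**What to change.** 1. **Record** an anonymous operator code and experience level for every case, and tabulate method by operator.
2. **Time outcomes** (log scale if skewed): fit method plus anaesthetist. Where operators use more than one method, enter anaesthetist as a fixed block, since this removes stable operator differences even when preference tracks skill. The alternative is a random intercept with Kenward-Roger or Satterthwaite degrees of freedom, named in the SAP.
3. **Attempts and categorical outcomes:** use an operator-stratified analysis, for example a Cochran-Mantel-Haenszel test, in place of the plain chi-square or Fisher test.
4. **If operators use only one method:** state that method and operator cannot be separated and that the 80% power for 93 patients does not apply.
5. **Reconcile** the preference sentence with the description of random groups. If patients are to be randomised, allocate within anaesthetist and keep the block. The gain is then mainly a modest increase in power.

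**Cost:** two items on the data form, one table and a short SAP section. The real price is statistical: wider intervals and lower power than the stated 80% when operators are nested in methods (54%, 34% and 14% at operator level in the 12-, 9- and 6-operator scenarios above). The sample size would then need to be revisited once the number of anaesthetists is known. The operator code should be captured at the time of the case, as it may be hard to recover later.
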